## **ANNEX 3. ADDITIONAL INFORMATION**

Not applicable

3. LIST OF ABBREVIATIONS

ACE inhibitor	Angiotensin converting enzyme inhibitors
ADR	Adverse drug reaction
AE	Adverse event
ARB	Angiotensin-receptor blockers
ATC	Anatomical, Therapeutic, Chemical classification system
COPD	Chronic obstructive pulmonary disease
DBP	Diastolic blood pressure
ICH	Intracranial haemorrhage
IQR	Interquartile range
MedDRA	Medical Dictionary for Regulatory Activities
NOAC	Non-Vitamin K antagonist oral anticoagulants/ New Oral Anticoagulants
NSAID	Nonsteroidal anti-inflammatory drug
NVAF	Non-Valvular Atrial Fibrillation
PT	Preferred Term
SBP	Systolic blood pressure
SmPC	Summary of Product Characteristics
SOC	System Organ Class
TIA	Transient ischemic attack
VKA	Vitamin K antagonists

4. SYNOPSIS

4.1. TITLE OF STUDY

Non-Interventional, cross-sectional study to describe NOACs management in patients with non-valvular atrial fibrillation (NVAF) in Spain. RE-CONOCE Study

4.2. STUDY NUMBER

1160-0287 - BOE-NOA-2017-01

4.4. OBJECTIVES

This study has been designed in order to describe the current anticoagulation management in Spain.

❖ **Primary objective:**

- ☞ The primary objective of the study is to describe the usage of NOACs in patients with NVAF, in the hospital setting, based on the baseline characteristics at the time of first NOAC initiation.

❖ **Secondary objectives:**

- ☞ To evaluate the appropriateness of prescribed therapy based on Spanish health authorities' recommendations (positioning therapeutic report).
- ☞ To describe NOAC treatment management.
- ☞ To describe the patient's knowledge about anticoagulant treatment, independent of NOAC type.

4.5. STUDY DESIGN

- ❖ **Design:** This is an observational, multicenter, cross-sectional study based on newly collected data that will be conducted in cardiology departments, in at least 102 centers in Spain
- ❖ **Study disease:** Non-Valvular Atrial Fibrillation
- ❖ **Study medication:** NOACs (BI NOAC: Dabigatran etexilate-Pradaxa®)

"Non-interventional, cross-sectional study to describe NOACs management in patients with non-valvular atrial fibrillation (NVAF) in Spain"

4.6. NUMBER OF PATIENTS

It is planned that a total of approximately 1000 patients, with NVAF currently on NOAC treatment and having initiated their first NOAC starting from November 2016 (Health Authorities positioning report publication), will be recruited for the study.

To minimize selection bias at the patient level, 10 consecutive patients from each site who meet entry criteria will be enrolled.

Cardiology departments, in a hospital setting, who regularly prescribe NOACs for stroke prevention in NVAF patients, will be selected to participate. The study will be performed among all the national territory.

4.7. STUDY POPULATION

To be eligible to participate in the study, patients must meet the following selection criteria.

The patient will be considered included when he/she agrees to participate in the study by signing the informed consent.

Patients, in the hospital setting, will be included in the study if all of the following criteria are met:

1. The patient is willing and provides written informed consent to participate in this study
2. The patient is at least 18 years of age
3. The patient has a diagnosis of non-valvular atrial fibrillation
4. The patient is on treatment with NOAC according to its approved local SmPC and has initiated his first NOAC starting from November 2016

Patients will be excluded from participating in this study if they currently participate in any clinical trial of a drug or device.

4.8. OUTCOMES

❖ Primary outcomes

- Usage of NOACs, in patients with NVAF, in the hospital setting, based on the baseline characteristics at the time of first NOAC initiation.

❖ Secondary outcomes

- The reasons for NOAC initiation collected during the study visit (at the time of patient enrollment).
- NOAC treatment management.
- Patient's knowledge about his condition.

5. GENERAL STATISTICAL METHODOLOGY

The content of the clinical database shall be transferred to SAS® data files for the statistical analysis. All the statistical analyses will be conducted using the statistical program SAS®v9.3 (SAS Institute Inc., Cary, NC, USA).

Description analyses of all the variables collected should be carried out. Depending on the type of variable, the following shall be presented:

- The categorical variables shall be summarized through frequencies and percentages.
- The continuous variables shall be summarized through measures of central tendency and dispersion: mean, standard deviation, median, interquartile range and extreme values (minimum and maximum).

The variables included in the study objectives will be summarized overall and by factors of interest.

The analysis population will consist of all eligible patients (i.e. all patients fulfilling all inclusion criteria and no exclusion criteria).

If patients have missing values for an outcome, those patients will be excluded for that outcome's analysis. No type of imputation shall be made to the data and the data will be considered as missing.

The primary outcome is the usage of NOACs, in patients with NVAF, in the hospital setting, based on the baseline characteristics at the time of first NOAC initiation. Baseline (at time of first NOAC initiation) variables will be analysed descriptively by NOAC type. Treatment groups will be defined according to first NOAC prescribed.

Standardized differences between Dabigatran Etexilate and each of the other NOACs separately will be estimated for these variables (baseline characteristics). The formulas are:

For means:
$$d = \frac{(\bar{x}_{DE} - \bar{x}_C)}{\sqrt{(s_{DE}^2 + s_C^2)/2}}$$

For proportions:
$$d = \frac{(\hat{p}_{DE} - \hat{p}_C)}{\sqrt{\frac{\hat{p}_{DE}(1 - \hat{p}_{DE}) + \hat{p}_C(1 - \hat{p}_C)}{2}}}$$

Where DE is dabigatran etexilate and C is the comparator

Standardized differences higher than 10% (in absolute value) are indicative of imbalance between the compared groups.

The secondary outcomes will be carried out descriptively for the total sample, regardless of the type of NOAC prescribed to the patient.

These objectives include: evaluating whether the recommendations of the Spanish health authorities have been followed, describing the management of the treatment with NOAC and evaluating, through a simple questionnaire of 4 questions, the knowledge the patient has about his illness and the treatment the patient is receiving.

The adverse drug reactions (ADR) and fatal adverse events (AE) shall be tabulated by System Organ Class (SOC) and Preferred Term (PT) using the Medical Dictionary for Regulatory Activities version 21 (MedDRA). A description of them shall be carried out: serious, relation, action taken, outcome, etc.

6. INCLUDED PATIENTS

The analysis population will consist of all eligible patients (i.e. all patients fulfilling all inclusion criteria and no exclusion criteria).

The following should be provided:

- ➔ Number of patients included in the study. Patients not included in the analysis will be shown in a table describing all protocol deviations.
- ➔ Number of patients included in each of the centers. The recruiting investigators within each participating center should be listed.
- ➔ Number of patients included by autonomous community.
- ➔ Number of patients included by type of NOAC and dose (first NOAC prescribed).

7. DESCRIPTION OF THE SAMPLE

7.1. DEMOGRAPHIC DATA

The quantitative variables will be described through the mean, median, standard deviation, interquartile range, minimum, maximum and the total number of patients with available data. These variables include:

- Age (years)

The qualitative variables will be described through their relative and absolute frequency distribution. These variables include:

- Sex
 - Male
 - Female

- Work status
 - Active
 - Inactive
 - Student
 - Retired
 - Not available
- Life status
 - Married
 - Single
 - Widower/widow
 - Divorced
 - Not available

7.2. PHYSICAL ASSESSMENT

The following should be provided, as continuous variables:

- Weight (Kg)
- SBP (mmHg)
- DBP (mmHg)

The number and percentage of patients that perform any physical activity should be provided.

7.3. CLINICAL HISTORY

The following should be provided:

- Number and percentage of patients depending on alcohol consumption: no consumption, moderate or high.
- Number and percentage of patients who presented or not concomitant diseases. Number and percentage of patients who presented or not each one of the following concomitant diseases:
 - ❖ Ischaemic stroke or TIA
 - ❖ Systemic embolism
 - ❖ Heart failure
 - ❖ Coronary artery disease
 - ❖ Ischaemic cardiomyopathy
 - ❖ Left ventricular dysfunction
 - ❖ Cerebrovascular disease
 - ❖ Renal disease
 - ❖ Liver disease
 - ❖ Bleeding
 - ❖ Other
 - ❖ Hypertension
 - ❖ Diabetes Mellitus
 - ❖ Hyperlipidaemia
 - ❖ COPD
 - ❖ Gastric and/or duodenal ulcer
 - ❖ Dementia
 - ❖ Anaemia
 - ❖ Rheumatic disease
 - ❖ Cancer
 - ❖ Prosthetic heart valves

In those patients who present other disease, not predefined, these should be detailed. They will be encoded through MedDRA dictionary based on PT and SOC.

7.4. CURRENT MEDICATION

In the same way as in the previous section, the number and percentage of patients who were or not receiving some other concomitant treatment will be provided.

A detailed description of the treatment will be made according to:

- ❖ ARB or ACE inhibitor
- ❖ Beta-blocker
- ❖ Calcium channel blockers
- ❖ Diuretics
- ❖ Amiodarone
- ❖ Statin
- ❖ Proton-pump inhibitor
- ❖ H₂ - receptor antagonist
- ❖ Aspirin
- ❖ Other antiplatelet agents
- ❖ Digoxin
- ❖ NSAID
- ❖ Verapamil/dronedarone
- ❖ Other antiarrhythmic
- ❖ Ketoconazole (systemic)
- ❖ Cyclosporine
- ❖ Litraconazole
- ❖ Other

The other non-predefined concomitant medication should be detailed. The other concomitant medication will be encoded through the ATC system code classification based on the active principal and the therapeutic group (first anatomical level).

7.5. LABORATORY

The number and percentage of patients that had performed a laboratory test before the first NOAC will be provided, specifically if available data on renal function and hepatic function.

For kidney function, creatinine clearance (obtained from medical charts or auto-calculated by Cockroft-Gault equation) shall be described as continuous variable. And for liver function, the distribution of the following parameters will be described as continuous variables: AST, ALT and total bilirubin.

7.6. NON-VALVULAR ATRIAL FIBRILLATION DIAGNOSTIC

The time since when the patient was diagnosed NVAF until the date of starting the first NOAC shall be summarized for all patients and then separately for patients who received previous VKA treatment and patients who were directly treated with a NOAC.

The age at which the patient was diagnosed will also be provided.

7.7. PREVIOUS TREATMENT WITH VITAMIN K ANTAGONISTS

The number and percentage of patients who were treated previously with VKA (acenocumarol or warfarin), the time in treatment with them, the time from withdrawal to start first NOAC and the reasons for VKA switch will be provided.

8. PRIMARY OBJECTIVE

The main endpoint is the usage of NOAC in patients with NVAF, in the hospital setting, based on the baseline characteristics at the time of the start of the first NOAC. These baseline variables will be analyzed descriptively by type of NOAC. The treatment groups will be defined according to the first NOAC that has been prescribed.

Standardized differences between Dabigatran Etexilate and each of the other NOACs separately will be estimated for these variables. These variables are: age at the time of the first NOAC initiation, CHA₂DS₂-VASc Score and HAS-BLED Score.

In order to answer the primary objective to complement the three primary variables, the following baseline characteristics (covariates) will be also analyzed descriptively by type of NOAC:

- Demographic characteristics (gender, work status, life status)
- Alcohol consumption
- Physical activity
- Weight
- Systolic BP/Diastolic BP
- AF diagnosis date (time from diagnosis to first NOAC initiation, months)
- Duration of previous VKA treatment, if applicable
- Reasons for VKA treatment switch
- Kidney function
- Liver function
- Concomitant and relevant previous diseases
- Concomitant treatments

8.1. AGE AT THE TIME OF THE FIRST NOAC INITIATION

The age at the time of the start of the first NOAC will be calculated as the difference between the start date of the first prescribed NOAC and the date of birth of the patient.

Once calculated, the age will be described in terms of central tendency and dispersion providing mean, median, standard deviation, minimum, maximum and interquartile range for all patients and by type of first prescribed NOAC.

8.2. CHA₂DS₂-VASc SCORE

The CHA₂DS₂-VASc score is clinical prediction rule for estimating the risk of stroke in patients with atrial fibrillation, a common and serious heart arrhythmia associated with thromboembolic stroke. Then this score is used to determine whether or not anticoagulation therapy is required.

A high score corresponds to a greater risk of stroke, while a low score corresponds to a lower risk of stroke.

In this sense, the total score will be described as a quantitative variable through its mean, median, standard deviation, minimum, maximum, IQR and number of patients with non-missing values.

The total score shall be stratified by category according to the following classification, providing the relatives and absolutes frequencies:

- Low risk (score 0 in male; score 1 in female)
- Moderate risk (score 1 in male; score 2 in female)
- High risk (score ≥ 2 in male; score ≥ 3 in female)

Note: *In the last update of European Society of Cardiology (ESC) guidelines 2016 the "female gender" is no longer considered by itself as an increase of the risk.*

8.3. HAS-BLED SCORE

The HAS-BLED score was developed as a practical risk score to estimate the 1-year for major bleeding in anticoagulated patients with atrial fibrillation and to identify potentially correctable bleeding risk factors such as uncontrolled hypertension, labile INRs, concomitant aspirin use and alcohol excess.

A high HAS-BLED score (≥ 3) is indicative of the need for regular clinical review and follow-up, but should not be used per se as a reason for stopping oral anticoagulation. Indeed, a high HAS-BLED score allows the clinician to 'flag up' patients at potential risk for serious bleeding.

The total HAS-BLED score will be described as a quantitative variable through its mean, median, standard deviation, minimum, maximum, interquartile range and number of patients available.

The total score shall be stratified by category, according to the following classification, and shall be provide the distribution of the relatives and absolutes frequencies:

Score	Bleeding risk*
0	Low risk
1-2	Intermediate risk
≥ 3	High risk

* The risk is based on the possibility of developing a hemorrhagic process (intracranial hemorrhage, hemorrhage requiring hospitalization or transfusion or a decrease in hemoglobin $> 2\text{ g/l}$)

9. SECONDARY OBJECTIVES

9.1. APPROPRIATENESS OF NOACs PRESCRIPTION

First of all, appropriateness of NOAC prescription based on national recommendations (positioning therapeutic report) is planned, for the entire eligible patients. For this, it will be reviewed if the presence of at least one of the below clinical situations or situations related to INR control were met.

- Patients with known hypersensitivity or with specific contraindications to the use of acenocoumarol or warfarin.
- Patients with a history of intracranial hemorrhage (ICH) (except during the acute phase).
- Patients with ischemic stroke who present high-risk clinical and neuroimaging criteria for ICH.
- Patients on VKA treatment who suffer from severe arterial thromboembolic events despite good INR control.
- Patients who have started treatment with VKA in which it is not possible to maintain INR control within range (2-3) despite good therapeutic compliance.
- Impossibility of access to conventional INR control.
- Other reason
- Unknown

The reasons for initiation of the first NOAC will be described in first place, broken down between clinical reasons or situations related to INR control. In case of other reason, it should be specified.

9.2. NOAC TREATMENT MANAGEMENT

A description of the first prescribed NOAC and other NOACs (if applicable) will be made, indicating:

- ✓ Number and percentage of patients according to NOAC type and dose
- ✓ Time in treatment calculated as the difference between start date and end date, if both are available and in other case informed consent date will be used (time to beginning study); it will be described as quantitative variable.
- ✓ NOAC Dose; it will be described as qualitative variable.
- ✓ Number and percentage of patients who need discontinue treatment or dose adjustment or change a new NOAC; in this case, reason for change.
- ✓ Number and percentage of patients who change other NOAC, including type of new NOAC or new doses, time in treatment if start and end dates, and time after first NOAC.

On the other hand, frequency of visits to the physician will be assessed quantitatively and qualitatively.

A descriptive analysis of the history of thromboembolic and hemorrhagic events presented by the patients will be carried out. First, the number and percentage of patients with or without thromboembolic and hemorrhagic events would be provided. A description will be made of the type of event suffered, if it was related to NOAC and as well as the number of times, for the following two types of events:

Thromboembolic events:

- TIA
- Ischaemic stroke
- Haemorrhagic stroke
- Embolism systemic
- Deep vein thrombosis
- Pulmonary embolism
- Stable angina
- Unstable angina
- Myocardial infarction without ST segment elevation
- Myocardial infarction with ST segment elevation

Bleeding events:

- Intracranial
- Digestive
- Genitourinary
- Gingival
- Nasal
- Pulmonary
- Articular-muscular
- Conjunctival
- Other

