Protocol date: 24 Jul 2017	Study number: 1160-0287	Version/Revision:	Version/Revision date:

and analysis.
 
Since the study is descriptive, the variables included in the study objectives will be summarized overall and by factors of interest. All results will be summarized with measures of central tendency (mean and median), variability/dispersion (standard deviation and interquartile ranges), absolute and relative frequencies, and ranges.
 
The analysis population will consist of all eligible patients (i.e. all patients fulfilling all inclusion criteria and no exclusion criteria). If patients have missing values for an outcome, those patients will be excluded for that outcome's analysis. Missing data will not be imputed.
			
Milestones:	

- Final Protocol: Jul 2017

- Start of data collection: November 2017

- End of data collection: May 2018

- Final study report: October 2018

		

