### **9.3 VARIABLES**

#### **9.3.1 Exposures**

Patients in this study will have been prescribed a NOAC treatment for their NVAF and initiated it in the time period from November 2016 to present. Prescription of the treatments will have been done under the sole responsibility of the healthcare professional and before the study visit. The study population will be treated with NOAC according to the approved local Summary of Product Characteristics (SmPC).

As this is a non-interventional observational study, designed to reflect as faithfully as possible real-life clinical practice, the decision to start treatment with NOAC is prior to and independent of the participation of the patient in the study and based on medical judgment criteria and routine clinical practice. In addition, no intervention, either diagnostic or therapeutic, will be applied to patients other than that used for routine clinical practice.

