## **9.9 LIMITATIONS OF THE RESEARCH METHODS**

A NIS is the most suitable design to obtain information about the use of medicines in everyday therapeutic practice and thus for investigating questions in everyday therapeutic practice. However, there are some limitations inherent to this design.

Consecutive enrolment will be employed to minimize selection bias. The entry criteria are less restrictive than the ones of a randomized clinical trial, which will permit the enrolment of a broader patient population.

The choice of NOAC was done before the study visit and it is done at the discretion of the investigator. However, as the setting is limited to the hospital setting (Cardiology Services), patients treated in other clinical settings will not be part of this study. Patients seen by their physician less than twice per year are therefore less likely to be included in the study. Patients with higher frequency of visits are more likely to be included in the study and could be over-represented in the sample. Additionally, having 10 patients recruited in each site, patients from the larger practice hospitals will also be under-represented.

As patients are included after first NOAC initiation and need to be treated by a NOAC at time of enrolment, any patient having prematurely discontinued any NOAC treatment between the time of first NOAC initiation and the start of the enrolment period will not be included in the study. The sample may therefore not be representative of all patients having initiated a NOAC since November 2016.

Channeling bias is a form of confounding that occurs when a drug is preferentially prescribed to patients with different baseline characteristics. Standardized differences will be applied when assessing channeling bias.

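### SAP 9.2's time in treatment is time on NOAC up to the visit, not course duration; the consent date should only censor courses confirmed as running, and the change percentages need a time base

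*SAP*

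**What the plan says.** SAP 9.2 takes time in treatment as end date minus start date "if both are available and in other case informed consent date will be used (time to beginning study"), and adds that "it will be described as quantitative variable". The rule sits under an introduction that covers the first NOAC and any later ones. The last bullet, on patients who switch, words it differently: "time in treatment if start and end dates, and time after first NOAC". Changes are reported as "Number and percentage of patients who need discontinue treatment or dose adjustment or change a new NOAC", with no time horizon and no person-time.

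SAP section 5 summarises continuous variables by mean, SD, median, IQR and range, and rules out any imputation.

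On who is observed and for how long:
- Protocol 9.9: patients "need to be treated by a NOAC at time of enrolment".
- Protocol 9.3.1: patients "initiated it in the time period from November 2016 to present".
- Protocol section 4, milestones: "Start of data collection: November 2017" and "End of data collection: May 2018".
- Protocol 9.3.2.2: the window for treatment management runs from first NOAC start to the study visit.
- Protocol Annex 2, comment under Section 3: the study performs no measures of occurrence.

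**The concern.** A course still running at consent has no completed duration. Its value under SAP 9.2 is the time since it started, so it is a right-censored observation. Summarising it with completed courses gives one mean and one spread. From these a reader cannot tell which part is duration and which part is only how long ago the patient started.

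The fallback depends on the end date being absent, not on the course being in progress. A course that ended without a recorded end date is therefore extended to consent.

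The percentages with a dose change or switch count events over windows of different length. They answer how many patients had changed by the visit. They do not by themselves say how fast change occurs. Describing NOAC treatment management is a stated secondary objective, and these are its duration and change figures.

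**Working it through.** The documents give no change rates, start-date distribution or treatment times, so there is no stated figure to reproduce. Steps 1 to 3 follow from the text. Steps 4 to 6 rest on assumptions.

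**1. Observation window.** The earliest start is 1 November 2016 and visits run from November 2017 to May 2018. The longest possible time since start is 1 November 2016 to 31 May 2018, 18.9 months; the shortest is near 0.

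**2. Share of running courses.** Each patient should have one running course at the visit. With m completed courses per patient on average, the running share of all courses is 1/(1 + m), a majority unless m exceeds 1. For first courses alone, it is a majority unless half or more have ended.

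**3. The two rules in SAP 9.2.** A patient who has switched and is still on the new NOAC has no end date for it. The general rule gives consent minus start. The last bullet, read literally, gives nothing and keeps only later courses that have already ended. The two need reconciling.

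**4. Scenarios (assumed).** Consent c is uniform on 12 to 19 months after 1 November 2016. Start = B·c, with B from Beta(1,2) (mostly early), uniform, or Beta(2,1) (mostly late). Elapsed time is E = c − start. With mean c = 15.5, mean E = 15.5 × 2/3, 1/2, 1/3 = 10.3, 7.75, 5.2 months. Change time T is exponential with 12-month incidence p, so λ = −ln(1 − p)/12. Any change is taken to end the course, since the SAP does not define this. The SAP value is Y = min(E, T); the crude percentage is P(T ≤ E).

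At p = 20%, λ = 0.2231/12 = 0.01860 per month, so the underlying mean course is 1/λ ≈ 54 months and the median 37 months. Simulation with 2 million patients per scenario gives:

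| | early | uniform | late |
|---|---|---|---|
| Pooled mean Y (months) | 9.28 | 7.05 | 4.81 |
| Running courses only, mean | 10.04 | 7.36 | 4.91 |
| Completed courses only, mean | 5.6 | 5.0 | 3.8 |
| Crude % changed | 17.3 | 13.1 | 8.9 |

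Check: for an exponential T, mean Y = P(T ≤ E)/λ. For uniform starts, 0.131/0.01860 = 7.04, which agrees to rounding.

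**5. What drives each figure.**
- *Pooled mean.* Start pattern at p = 20% moves it by 9.28 − 4.81 = 4.5 months. Moving p from 0 to 40% with uniform starts moves it only from 7.75 to 6.3, or 1.5 months.
- *Crude percentage.* It follows p more: 0, 13.1 and 26.8% for p = 0, 20 and 40% with uniform starts. Start pattern still moves it about two-fold (17.3/8.9 = 1.9). A crude 13% would arise from p = 15.1% (early), 19.8% (uniform) or 28.5% (late).
- *If only switches end a course and are half of all changes.* Then 91 to 95% of courses are running, and pooled means are 9.8, 7.4 and 5.0 months.

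**6. With a time base.** Kaplan-Meier at 12 months returns 20% in all three patterns, including with falling or rising hazards (Weibull shapes 0.6 and 1.5). Events per 100 patient-years are 22.3 throughout if the rate is constant. With shape 0.6 they move to about 24, 26 and 30, and with shape 1.5 to about 21, 20 and 17. With n = 1000 and uniform starts, the Kaplan-Meier SE is 1.1 points at 6 months (about 540 at risk) and 1.8 points at 12 months (about 170 at risk). With late starts, about 45 are at risk at 12 months and the SE is 2.65 points.

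**The case against.** Time on treatment up to the visit is a legitimate cross-sectional description. Protocol 9.3.2.2 sets that window, and SAP 9.2 labels the substituted value as time to study start. Nothing in either document presents it as persistence. Pooling itself moves the mean little: 7.05 against 7.36 months for running courses alone with uniform starts. The large spread in the scenarios comes from different hypothetical start patterns, and a single study has only one. Secondary outcomes are described for the total sample, so no planned comparison between NOACs is distorted. Annex 2 disclaims measures of occurrence, and Kaplan-Meier does not repair the selection that Protocol 9.9 already admits.

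Most of this stands, and it limits the point in three ways:
- A reader might infer that the change percentages are wrong. They are not; they validly describe change up to the visit and lack only a time base.
- A reader might infer that separating completed from running courses yields course duration. It does not. Completed courses are truncated at the visit and average about 4 to 6 months in the scenarios, against an underlying mean of about 54 months.
- Events per patient-year is not an equivalent remedy unless the rate is constant.

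The objection does not answer three things: the pooled output does not separate time to date from duration, the fallback does not check that a course is running, and the two rules in 9.2 differ.

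**Conclusion.** The point holds in limited form. From the text alone, the planned summary is time on treatment to date, mostly censored and bounded at about 19 months. The consent-date fallback also reaches ended courses with a missing end date, and SAP 9.2 has two rules for later NOACs.

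The size is conditional. With the assumed windows and a constant 20% 12-month change rate, the crude percentage is about 9 to 17% and the pooled mean 4.8 to 9.3 months, depending on start pattern.

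A reader might go further and conclude that the pooled figure is known mainly to reflect start dates. The documents do not establish that. It holds for spread-out starts and modest change rates, and weakens with frequent change or tightly clustered starts. The outcome is secondary and descriptive and the primary objective is untouched, but the correction is cheap and worth making.

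**What to change.** In SAP 9.2:

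1. Use the consent date only for courses confirmed as running at the visit, and treat it as a censoring date. Treat an ended course with no end date as missing. Apply one rule to first and later NOACs, reconciling the last bullet with it.
2. Label the planned summary *time on treatment to the study visit*. Report the distribution of time since first NOAC and the numbers of running and ended courses. If the duration of ended courses is shown, state that it is truncated at the visit and does not estimate course length.
3. Beside the planned percentages, give a descriptive Kaplan-Meier or cumulative incidence of first dose change and of first switch at 6 months, and at 12 months where numbers allow, with numbers at risk. Label it as conditional on NOAC use at the visit, and align the Annex 2 comment. Do not offer events per patient-year as an equivalent unless a constant rate is assumed.

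The cost is SAP wording and one standard SAS procedure on dates that Protocol 9.3.2.2 already collects. The downsides are slightly more analysis work, few at risk at 12 months if starts were late, and possible bias if stopping all NOACs is related to change. In one assumed case (uniform starts, 30% of patients with 2 or 4 times both hazards, 30% stopping by 12 months), Kaplan-Meier at 12 months gives 19.4% or 17.3% instead of 20%. The crude percentage shifts too, from 13.1% to 11.8% or 10.7%.
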